BRV (tablet and oral solution) should be administered twice daily (bid) in 2 equally divided doses. All LTFU subjects must be able to tolerate the minimum dose specified in the core study to be eligible for entry into the Evaluation Period of N01266. All DE subjects must be able to tolerate at least 1mg/kg/day during the Up-Titration Period prior to entering the Evaluation Period of N01266.

The maximum allowable BRV dose is 5.0mg/kg/day (2.5mg/kg bid), not to exceed a dose of 200mg/day. Subjects will receive oral solution or tablets, as appropriate. With the exception of dose adjustments for BRV during the Up-Titration Period, which should be made in accordance with the protocol-specified guidelines, dose adjustments of BRV and any concomitant antiepileptic drugs (AEDs) are allowed at any time based on clinical judgment.

Subjects will receive BRV treatment in this study for at least 3 years, until approval of BRV has been obtained for pediatric subjects in their age range, until a managed access program is established as allowed per country-specific requirements in addition to legal and regulatory guidelines, until subjects transition to another BRV study, or until the investigational product development in the related age range of the pediatric population is stopped by the Sponsor, whichever comes first.

For LTFU subjects, the EV is the first study visit. For DE subjects, the EV occurs after subjects have completed the ScrV and at least 1 Titration Visit (TV), and have maintained acceptable tolerability and seizure control on the same daily dose of BRV (no lower than the minimum specified dose) for 7 ± 2 days of the Up-Titration Period. For subjects who continue in this study until it ends, the Evaluation Period will extend from the EV until the final evaluation visit (Final Visit, FV). For subjects who prematurely discontinue the study, the Evaluation Period will last from the EV until the Early Discontinuation Visit (EDV), followed by a maximum 4-week Down-Titration Period, a 2-week Safety (Drug-Free) Period, and a final Safety Visit (SV). Subjects already enrolled in N01266 may participate in EP0065 (an intravenous [iv] BRV study for pediatric subjects), if eligible, and then resume participation in N01266.

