In case of early discontinuation, after the EDV, or for subjects who complete the study but do not continue BRV treatment, the Down-Titration Period starts with scheduled Down-Titration Visits (DTV). Dose will be down titrated by a maximum of half the dose every week for a maximum of 4 weeks until a dose of 1mg/kg/day is reached.

After 2 weeks free of study drug, the Safety Period, subjects will complete the Safety Visit (SV).

The study is defined to be completed if the study status on the study termination form is marked as completed. This indicates that all planned visits have taken place. Planned visits are dependent on whether a subject discontinues the study or not, and on whether a subject goes into another study or takes marketed drug after FV.

At each visit, the subject/parent(s)/legal representative(s) will receive a DRC, which has to be filled in daily by parent(s)/legal representative(s) or subject, if applicable, and returned at the next visit. No DRC will be dispensed at the SV or the FV.

The date and the number of epileptic seizures will be recorded on the DRC, as well as the type of seizure (according to individual description of seizures), occurrence of clusters, intake of concomitant AEDs, undesirable events with start and end dates, health care provider consultations not foreseen per protocol, and changes in concomitant medication, if applicable.

The written information will be discussed with the subject/parent(s)/legal representative(s) at each visit in order to ensure completeness and accuracy. As a result of the discussion, the Investigator will assess the seizures according to the International League Against Epilepsy (ILAE) codes and record the seizure types and frequency on the electronic case report form (eCRF); he/she will also confirm the presence of AEs (if applicable). Concomitant medication changes, health care provider consultations not foreseen per protocol, and AEs will be reported by the Investigator on the specific pages of the eCRF.

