3.2.3 Study periods

[Table 3–1](#) shows which study periods are applicable to DE and LTFU subjects:

This document cannot be used to support any marketing authorization application and any extensions or variations thereof.
PUBLIC COPY

Table 3-1: Study periods

Period		Screening Period	Up-Titration Period			Evaluation Period							Down-Titration Period	Safety Period		
Subjects	Visit	ScrV	TV1	TV2	TV2	EV	MEV	FEV	MEV	FEV	MEV	YEV	...	FV/EDV	DTV	SV
			V1	V2	V3	V4	V5	V6	V7	...						
Subjects	DE	x	x	x	x	x	x	x	x	x	x	x	x	x	(x)	(x)
	LTFU					x	x	x	x	x	x	x	x	x	(x)	(x)
	Early Discontinuations												x	x	x	x

(x) – only applicable if the subject does not switch to another BRV study or is taking marketed drug after FV

The study is divided into 5 periods: Screening Period, Up-Titration Period, Evaluation Period, Down-Titration Period, and the Safety Period.

There is a Screening Period for all DE subjects. For DE subjects, this comprises assessments performed prior to the first dose of BRV in N01266. So start date of Screening Period is date of written informed consent and end date is the day before first dose of BRV (TV1-1). Although, patients in LTFU studies will not attend a screening visit, the screening information comprises information collected at various assessments during the core study and consequently will have been collected at different times depending on the domain. Domain specific information is detailed in Section 3.3.

The Up-Titration Period is only applicable to DE subjects, and the start date is the date of the first dose of BRV. The following algorithm is used to determine the end date:

- If the subject enters the Evaluation Period, the date 1 day prior to the EV is the end date
- If the subject does not enter Evaluation Period, the Up-Titration Period ends on the date of the final dose of BRV

For the Evaluation Period, the start date is the date of the first dose of BRV on or after the EV date, and the following algorithm is used to determine the end date:

- If the subject continues the study until it ends, the Evaluation Period ends on the date of FV
- If the subject prematurely discontinues the study, the date of EDV is the end date

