A discontinued subject or a subject who completes the study but does not continue BRV treatment will be considered entering the Down-Titration Period only if the subject has a record of at least 1 dose of BRV after the date of EDV. The start date of the Down-Titration Period is set as 1 day after the date of EDV, and the Down-Titration Period ends on the date of the final dose of BRV (DTV).

A discontinued subject without any dosing of BRV after the EDV will not have participated in the Down-Titration Period, and no artificial Down-Titration Period will be created for the purpose of analysis.

A discontinued subject is considered to have entered the Safety Period if the subject has at least 1 contact (scheduled visit, unscheduled visit (UV), or telephone contact) after the date of the final dose (DTV). The Safety Period starts 1 day after the date of the final dose of BRV irrespective of entering the Down-Titration Period, and end date is the date of last contact with the subject.

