3.2.6 Last Value on BRV treatment

The Last Value on BRV treatment for all assessments is the final available result obtained after the first dose of BRV and prior to or on the date of the final dose of BRV within evaluation period. All scheduled and UV assessments within evaluation period will be considered. Last Value will be determined separately for each vital sign, ECG and laboratory parameter.

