The number and percentage of subjects with any post-Baseline PCST value, any PCST low value, and any PCST high value for hematology, biochemistry and urinalysis will be summarized for the Evaluation and Safety Periods separately and for the Evaluation and Safety Period combined by laboratory parameter overall and by age group. PCST criteria for hematology and biochemistry are presented in Appendix Section 12.1 A urinalysis value is considered PCST abnormal if an upward shift of at least 2 degrees from the Baseline occurs under investigational treatment. Percentages will be relative to the number of subjects with an on-treatment assessment.

Observed values and change from Baseline value tables will only present scheduled visits, whereas for PCST tables, values reported at an UV will be summarized under the preceding scheduled visit if the abnormality was not already reported at the preceding scheduled visit. Treatment emergent for this analysis includes any PCST laboratory abnormalities observed during the Evaluation Period.

A subject number table will be provided that identifies subjects with a PCST finding after the first dose of BRV for each type of laboratory abnormality.

All laboratory parameters (planned and unplanned parameters and assessed on scheduled and unscheduled visits) will be provided in subject data listings.

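### The Safety Period column of the laboratory PCST summary uses subjects with an on-treatment assessment as its denominator, which understates the rate among those tested off drug

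*SAP*

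**What the plan says.** Section 8.3 of the SAP states that counts and percentages of subjects with any, low and high laboratory PCST values "will be summarized for the Evaluation and Safety Periods separately and for the Evaluation and Safety Period combined by laboratory parameter". The denominator is given once, in the same paragraph: "Percentages will be relative to the number of subjects with an on-treatment assessment". No separate rule is given for the Safety Period.

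Other parts of the SAP bear on what this means:

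- Section 2 describes "a 2-week Safety (Drug-Free) Period". Section 3.2.3 fixes its start: "The Safety Period starts 1 day after the date of the final dose of BRV irrespective of entering the Down-Titration Period".
- Table 3-1 in Section 3.2.3 marks the Down-Titration and Safety Visits as "only applicable if the subject does not switch to another BRV study or is taking marketed drug after FV". The wording is awkward. Read with Section 2.3.1, it means that subjects who go on to another BRV study or to marketed drug do not have these visits.
- Section 3.2.6, on the last value on BRV treatment, ends the on-treatment window "prior to or on the date of the final dose of BRV within evaluation period".
- The next paragraph of Section 8.3 adds: "Treatment emergent for this analysis includes any PCST laboratory abnormalities observed during the Evaluation Period".
- Section 3.9 defines PCST values more widely, as qualifying values at any time once screening is past and BRV has been started. Sections 8.3 and 12.2 define a urinalysis PCST as an upward shift of at least 2 degrees arising while the subject is on investigational treatment.

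**The concern.** A percentage is a rate only if the subjects in the denominator could have appeared in the numerator. For the Safety Period column the numerator comes from samples taken after the last dose, while the denominator is defined by samples taken during treatment. A subject who was tested on treatment but never tested in the Safety Period is counted as free of a Safety Period abnormality.

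The column would sit beside the Evaluation Period column, and readers will compare the two. A lower Safety Period figure could then be taken as abnormalities resolving off drug when it partly reflects subjects who were not sampled.

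The surrounding wording adds doubt about what the column should contain, because it ties treatment-emergence to the Evaluation Period and urinalysis PCST to time on treatment.

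**Working it through.** The SAP states no PCST rate and no expected number of Safety Visits, so there is no figure of its own to reproduce. The check is on the denominator.

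**Notation.** N = subjects with an on-treatment assessment of a parameter; m = those of them with a Safety Period assessment; x = subjects with a Safety Period PCST value.

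- As written: x / N.
- Among those tested in the period: x / m.
- Hence: as written = (x / m) × (m / N).

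The two agree only if m = N. Section 3.2.3 makes m < N the expected case, because subjects continuing BRV elsewhere have no Safety Visit. In addition, Section 3.2.3 treats a discontinued subject as having entered the Safety Period on the strength of a single contact, which may be a telephone call. Entry into the period therefore does not imply a blood sample.

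**Illustration.** Take N = 600, the approximate planned enrollment in Section 2, assuming that all have an on-treatment value. Assume a 10% PCST rate among those tested in the Safety Period. The ratio m/N is not in the SAP and is varied.

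| m/N | m | x = 0.10 × m | As written, x/600 | Among those tested, x/m |
|---|---|---|---|---|
| 10% | 60 | 6 | 1.0% | 10% |
| 20% | 120 | 12 | 2.0% | 10% |
| 50% | 300 | 30 | 5.0% | 10% |
| 80% | 480 | 48 | 8.0% | 10% |
| 100% | 600 | 60 | 10.0% | 10% |

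The factor is m/N whatever the rate. With an assumed 5% rate and m/N of 20%, x = 0.05 × 120 = 6, displayed as 6/600 = 1.0%.

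**The other two columns.** For the Evaluation Period, numerator and denominator come from essentially the same samples. For the combined column, the right denominator is everyone tested in either period. It differs from N only by subjects with a Safety Period value and no on-treatment value, who are likely to be few.

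**Comparison within the SAP.** Section 8.4.1 gives the by-visit vital-signs PCST percentages relative to subjects with a value at that visit. Section 8.4.2 does the same for ECGs by visit. Section 8.3 itself bases the urinalysis response-category percentages, including those at the Safety Visit, on subjects assessed at each time point. The laboratory PCST summary departs from this practice.

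**The case against.** The strongest reply is that the denominator sentence is a generic line that any programmer would apply sensibly. Section 3.1 says in general terms that denominators will suit the analysis, neighbouring tables are matched by time point, and on-treatment assessment is not defined for this table. This has some force as a prediction of what will be programmed. It does not repair the text: a general sentence does not override a specific one, and an assessment after the last dose cannot be called on-treatment under Section 3.2.3 or by analogy with Section 3.2.6.

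Other replies stand, and they limit the point:

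- A reader might infer that most treated subjects lack a Safety Period sample, or that the dilution is several-fold. The SAP gives no proportion. Section 2.3.1 sends early discontinuers, and completers who do not continue BRV, to the Safety Visit. The documents support some subjects without a sample, not most.
- A reader might infer that all three percentages are wrong. Only the Safety Period one is materially affected.
- A reader might infer that the treatment-emergent sentence excludes Safety Period values outright. It stands in the following paragraph, which deals with unscheduled visits, and it says what the term includes rather than what it is limited to. Section 3.9 already covers values after the last dose. The wording needs alignment, but it is not a flat contradiction.
- A reader might infer that a primary endpoint is at stake. The primary objective is long-term safety and tolerability, but Section 2.2.1 names only treatment-emergent and serious adverse events as primary variables, and Section 2.2.3 lists laboratory tests among the other variables.

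All summaries are descriptive. Counts are shown with the percentages, subjects with PCST findings are identified in a table, all laboratory data are listed, and Safety Visit values are summarized separately. A careful reader could recover the rate among those tested.

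**Conclusion.** The point holds for one column. As written, the Safety Period PCST percentage equals the rate among those tested multiplied by m/N, and it is understated whenever some subjects with on-treatment laboratory data have no Safety Period data. The direction follows from the SAP's own period definitions. The size does not: at an assumed 10% rate, the display would be 2%, 5% or 8% for m/N of 20%, 50% or 80%, and the effect disappears at 100%. Importance is minor to moderate, because no test or primary variable depends on the column and the underlying data are reported in full.

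**What to change.** In Section 8.3, replace the single denominator sentence with a rule per parameter and period: subjects with at least one post-Baseline assessment of that parameter in the period shown, and in either period for the combined column. Base it on having a result, not on having entered the period. Show that denominator beside each percentage.

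In the same edit, reconcile the treatment-emergent sentence in the next paragraph, and the on-treatment condition for urinalysis shifts in Sections 8.3 and 12.2, with the planned Safety Period summary and with the PCST definition in Section 3.9. The text should say plainly whether values after the last dose count as PCST for each test group.

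The cost is a few lines of SAP wording and a denominator change in one table program. No new data are needed.

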8.4 Vital signs, physical findings, and other observations related to safety

8.4.1 Vital signs

Vital signs, including measurements of blood pressure, supine or sitting pulse rate, and body temperature, are assessed after 5 minutes of rest at the ScrV, TV(s), and EV, MEV, FEV, YEV, FV, and at the EDV, Down-Titration Visit (DTV), and the SV in the case of early discontinuation. For LTFU subjects, at the EV, vital sign data will be obtained from the final visit of the core study (if available) and should not be recorded in the eCRF for N01266. If not available, vital signs data will be recorded within N01266 as for DE subjects.

Observed values and change from Baseline value for SBP, DBP, and pulse rate will be summarized for Baseline, EV, each visit during the Evaluation Period for which vital signs or body weight were assessed, EDV, Last Value on Treatment, FV, the Down-Titration Visit (DTV), and the Safety Visit (if available). This summary will be repeated separately for data collected during the Up-Titration visits for DE subjects.

The PCST criteria are based on FDA Division of Neuropharmacological Drug Products guidelines with some UCB-defined additions.

The number and percentage of subjects with any post-Baseline PCST value, any PCST low value, and any PCST high value will be summarized for SBP, DBP, pulse rate, and body weight. This summary will consider all assessments after the first dose of BRV and prior to or on the date of the final dose of BRV (excluding Up-Titration Assessments for DE Subjects). Percentages will be relative to the number of subjects with a post-Baseline assessment. This summary will be repeated for the Up-Titration Period for DE Subjects.

Additionally, the PCST table will be provided stratified by visit for all visits during Evaluation Period. Percentages will be relative to the number of subjects with a value at the corresponding visit.

A subject number table will be provided that identifies subjects with a clinically significant finding after the first dose of BRV for each type of vital sign abnormality.

All vital signs will be provided in subject data listings.

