During the Evaluation Period, Minimal Evaluation Visits (MEVs) and Full Evaluation Visits (FEVs) will be performed alternatively every month during the first 3 months and every 3 months thereafter, with a Yearly Evaluation Visit (YEV) every 12 months.

Safety variables include adverse events (AEs), safety laboratory assessments (hematology, biochemistry including hepatic monitoring of alanine aminotransferase [ALT], aspartate aminotransferase [AST], alkaline phosphatase [ALP], total bilirubin, and gamma-glutamyl transferase [GGT], and endocrinology for all subjects and urinalysis for subjects for whom sample collection is feasible), plasma concentrations of BRV and phenytoin (if applicable),

electrocardiograms (ECGs), vital signs, physical and neurological examinations, psychiatric and mental status, body weight, height, and head circumference.

All efficacy variables will be considered exploratory in nature. Seizure counts will be based on the daily record card (DRC) information or electroencephalograms (EEGs) and the disease characteristics of each subject.

Other variables include direct cost parameters (such as concomitant medications, medical procedures, health care provider consultations not foreseen by the protocol, and hospital stays) and the change in Achenbach CBCL (CBCL/1½-5 or CBCL/6-18), BRIEF-P/BRIEF, and PedsQL scores, and the change in Bayley-III scales for subjects enrolled in English-speaking countries and countries where a validated translation is available.

Up to 600 subjects may possibly enroll in this study. The number and location of sites will depend on those participating in core studies from which LTFU subjects will be enrolled, and those participating in direct enrollment. Sites of direct enrollment will include, but not be limited to, sites participating in core studies.

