2.2 Study variables

2.2.1 Primary variables

The primary variables include the following:

- Treatment-emergent AEs
- Treatment-emergent serious adverse events (SAEs)

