2.2.3 Other variables

For subjects ≥ 2 years of age (based on DRC data):

- Responder rate (the percentage of subjects who have a $\geq 50\%$ reduction in seizure frequency per 28 days from Baseline for POS)
- Absolute change in seizure frequency (total seizures) per 28 days from Baseline to the end of the Evaluation Period
- Percent change in seizure frequency (total seizures) per 28 days from Baseline to the end of the Evaluation Period
- Seizure freedom over the Evaluation Period
- Proportion of seizure-free days over the Evaluation Period

For subjects < 2 years of age or subjects with typical absence seizures based on DRC seizure counts:

- Seizure freedom rate over the Evaluation Period (all types) by visit and by time intervals (6 months, 12 months, etc.)
- Proportion of seizure-free days over the Evaluation Period (all types) and by time intervals (6 months, 12 months, etc.)
- Absolute worsening in ADF of total seizures (all types)
- Percent worsening in ADF of total seizure (all types)
- A descriptive summary of seizure frequency by visit based on the DRC data will be also provided for these subjects

In addition, for subjects < 2 years of age (based on EEG data [recorded at least 24 hours]) or subjects with typical absence seizures (based on EEG data):

- Responder rate for total POS defined as the percentage of subjects with a $\geq 50\%$ reduction in ADF of POS recorded on EEG
- Absolute change in ADF of total seizures (all types)
- Percent change in ADF of total seizures (all types)
- Seizure freedom (rate and proportion)
- Absolute worsening of other types of seizures
- Percent worsening of other types of seizures

For subjects with typical absence seizures:

- Number and type of non-absence seizures

For all subjects:

The other variables include the following:

- Physical examinations (including Tanner staging, if applicable depending on subject's development status)
- Neurological examinations
- Psychiatric and mental status
- Laboratory tests (hematology, biochemistry including hepatic monitoring of ALT, AST, ALP, total bilirubin, and GGT, and endocrinology [follicle-stimulating hormone, luteinizing hormone, thyroid-stimulating hormone, triiodothyronine, and tetraiodothyronine] for all subjects and urinalysis for subjects for whom sample collection is feasible)
- ECG
- Vital signs (blood pressure, pulse rate, and body temperature)
- Body weight
- Height and head circumference
- Plasma concentrations of BRV and phenytoin (if applicable)

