2.3.1 Study design for DE subjects

The screening period comprises the screening visit (ScrV).

Directly enrolled subjects will begin receiving BRV in the Up-Titration Period at Titration Visit 1 (TV1) after all inclusion and exclusion criteria are met. The BRV dose will be titrated to optimize tolerability and seizure control. Subjects may enter the Evaluation Period after they have remained on the same daily dose (no lower than the minimum specified dose) for 7 ± 2 days that, in the opinion of the Investigator, has demonstrated acceptable tolerability and seizure control. Up to 3 TVs may be needed before entry into the Evaluation Period.

Evaluation Period starts with the Entry Visit (EV) followed by Minimal Evaluation Visits (MEV), Full Evaluation Visits (FEV), Yearly Evaluation Visits (YEV), possibly Unscheduled Visits (UV) and Early Discontinuation Visits (EDV), if applicable. For more detailed information of visits scheduled, see [Table 2-1](#)

Table 2-1: Visit sequence

DE subjects		
	Visit	Type of visit
	ScrV	Screening
W1	TV1 ^a	TV
W2	TV2 ^a	TV
W3	TV3 ^a	TV

All subjects		
First year follow-up		
M0	V1	EV ^b
M1	V2	MEV
M2	V3	FEV
M3	V4	MEV ^c
M4	-	-
M5	-	-

M6	V5	FEV
M7	-	-
M8	-	-
M9	V6	MEV ^c
M10	-	-
M11	-	-
Second and subsequent years follow-up^d		
M12	V7	YEV
M15	V8	MEV
M18	V9	FEV
M21	V10	MEV
and every 3 months thereafter	V11, V12, etc.	YEV, MEV, etc.

BRV=brivaracetam; EV=Entry Visit; FEV=Full Evaluation Visit; LTFU=long-term follow-up; M=Month; MEV=Minimal Evaluation Visit; ScrV=Screening Visit; TV=Titration Visit; V=Visit; W=Week; YEV=Yearly Evaluation Visit

Note: Visits at W1, W2, W3, and M0 will occur 7 ± 2 days after the previous visit; visits at M1, M2, and M3 will occur 30 ± 7 days after the previous visit; visits at M6, M9, M12, M15, M18, M21 and every 3 months thereafter will occur 90 ± 15 days after the previous visit.

“-” denotes that no visit is scheduled in that month.

^a All DE subjects must participate in at least TV1, but may participate in fewer than 3 TVs as described in Section 7.2.1 of the protocol.

^b For LTFU subjects, the EV is the final evaluation visit of the core study. For DE subjects, the EV represents the point of entry into the Evaluation Period.

^c Hepatic monitoring tests only will be performed as described in Section 9.5.1 of the protocol.

^d Subsequent years will follow the same visit schedule.

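### SAP 8.4.1 leaves body weight out of the change-from-Baseline table, so for subjects under 17 the only post-Baseline weight summary is a growth-curve flag that ignores where the child started

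*SAP*

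**What the plan says.** Section 8.4.1 fixes the main vital-signs table: "Observed values and change from Baseline value for SBP, DBP, and pulse rate will be summarized for Baseline, EV, each visit during the Evaluation Period". The sentence goes on to pick the visits as those "for which vital signs or body weight were assessed". Weight therefore decides which visits appear but is not itself one of the tabulated parameters.

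The other planned table is the PCST count: "any PCST low value, and any PCST high value will be summarized for SBP, DBP, pulse rate, and body weight". It uses assessments from first to last dose, with the up-titration assessments of DE subjects reported separately. In addition, "the PCST table will be provided stratified by visit for all visits during Evaluation Period".

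The weight criterion is in Section 12.3. Below 17 years a weight is flagged if it lies outside 3% to 97% of the growth curve for sex and age on the day of weighing. From 17 years it is flagged for a change of 10% or more from Baseline. Section 3.9 counts any qualifying value after screening and after the first dose.

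Section 3.3 gives weight its own Baseline rule: the last value before BRV for DE subjects, and the last value up to the first core-study BRV dose for LTFU subjects. Section 3.2.9 maps early-discontinuation weights to scheduled visits.

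Section 2 names "body weight, height, and head circumference" among the safety variables, and Section 2.2.3 lists "Height and head circumference" among the other variables. Section 6.1 summarises weight, height and head circumference at Baseline only. Section 3.1 promises listings of all recorded and calculated data, including change from Baseline.

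**The concern.** The study follows children from 1 month of age for years, and its primary objective is long-term safety. Two questions about weight matter: did children move relative to their own starting point, and is a low or high weight on BRV new? For subjects under 17 the planned tables answer neither directly. The flag records where a child stands, not how far the child has moved. Because it takes no account of Baseline, its treatment-emergent label also covers children who were already outside the limits before BRV. A growth problem reported as an adverse event would appear in the Section 8.2 tables; a slow drift that nobody reports would not.

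**Working it through.** **1. The text side by side.** The SAP states no figure on this point, so the first check is which summaries exist.

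| Measure | PCST criterion | Change-from-Baseline table |
|---|---|---|
| SBP, DBP, pulse rate | Absolute limits by age (12.3) | Yes (8.4.1) |
| Hematology, biochemistry | Absolute limits (12.1) | Yes (8.3) |
| Urinalysis | Upward shift of at least 2 degrees from Baseline (8.3, 12.2) | Not needed for the flag; Baseline is built in |
| Weight, 17 years and over | 10% or more change from Baseline (12.3) | No, but Baseline is built in |
| Weight, under 17 | Growth-curve position (12.3) | **No** |

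Of these rows, only weight under 17 has neither a Baseline term in the flag nor a change table beside it.

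**2. Is there a pre-BRV comparator?** The PCST table uses post-dose assessments. The by-visit version covers Evaluation Period visits, and even an EV column would be on BRV: "For LTFU subjects, the EV is the final evaluation visit of the core study", and DE subjects reach EV only after up-titration. Section 6.1 does give Baseline weight, but in kg and not paired with later values.

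**3. Illustration at one visit.** Assumptions, none from the SAP: weight-for-age z-scores are normal with SD 1 and Baseline mean m; all children fall by d. For scale, 600 subjects (Section 2.3.4), all treated as under 17. The cut-off is c = Φ⁻¹(0.03) = −1.881.

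Low = Φ(c − m + d); High = 1 − Φ(−c − m + d).

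- m = 0, d = 0: 3.0% low, 3.0% high (18 and 18 of 600).
- m = 0, d = 0.5: Φ(−1.381) = 8.4% low, 1 − Φ(2.381) = 0.9% high (50 and 5 of 600).
- m = −0.5, d = 0: Φ(−1.381) = 8.4% low, 0.9% high, the same as the line above.

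A uniform fall does move the rows, but at a single visit a population that started light and did not change gives the same picture.

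**4. How many flags are old?** Let r be the correlation between the Baseline and visit z-scores, and J the bivariate normal probability of being low at both. Already-low share = J / P(low at visit). With m = 0, d = 0 and r = 0.90, J = 0.0181, so the share is 0.0181 / 0.0300 = 60%.

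| No change (d = 0) | r = 0.80 | r = 0.90 | r = 0.95 |
|---|---|---|---|
| m = 0 | 45% | 60% | 72% |
| m = −0.5 | 54% | 67% | 77% |

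**5. Does conditioning on Baseline help?** New-low rate = (P(low at visit) − J) / (1 − P(low at Baseline)). At r = 0.90:

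- Start −0.5, no change: (0.0837 − 0.0565) / (1 − 0.0837) = 3.0%.
- Start 0, fall 0.5: (0.0837 − 0.0270) / (1 − 0.0300) = 5.8%.

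Over r = 0.80 to 0.95 the ranges are 2.1% to 4.2% and 5.6% to 6.3%. The two cases, identical in step 3, now separate.

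**6. What the flag misses.** A child at the median must fall 1.88 SD to be flagged low. Among children who all fall 1 SD from m = 0, 1 − Φ(c + 1) = 1 − Φ(−0.881) = 81% are not flagged low at a given visit.

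**The case against.** A reader might infer that the report will hold no within-child growth data. It will: the listings in Section 3.1 include change from Baseline. What is missing is a tabulated summary.

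A reader might also infer that drift would be invisible, or could never be told from a light starting population. That goes too far. The comparison in step 3 is at one visit. Across visits, a stable light population would stay near 8.4% low, while a 0.5-SD drift would climb from about 3.0% to 8.4%. The by-visit table can show that. It still does not say which flags are new, and dropout changes who is in each column.

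Three further points count against a strong claim. Section 8.4.1 plans a table identifying subjects with clinically significant vital-sign findings; if it covers weight, flagged children could be checked against their listed Baseline. The PCST summary is repeated for the up-titration of DE subjects, which lasts up to 3 weeks and so is close to pre-drug for a slow measure, although it covers DE subjects only and is not paired with later values. Absolute limits are also the usual PCST convention in this SAP, so the weight criterion is not odd in itself; the difference is that no change table stands beside it.

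Nor are the weight Baseline and the early-discontinuation mapping unused: the rule at 17 and over, the listings and the by-visit flags draw on them.

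**Conclusion.** The point holds as a correctable gap in the planned summaries. Weight was apparently left out of the parameter list by oversight, and for subjects under 17 the remaining summary mixes new with pre-existing low or high weight under a treatment-emergent label. Under the stated assumptions, 45% to 72% of low flags at a visit would be pre-existing when nothing has changed (54% to 77% if the population starts 0.5 SD light). These figures rest on normal z-scores, the assumed correlations and a common shift, and on treating everyone as under 17, which is true at entry but not for those who turn 17 during follow-up. They show the size of the mixing and do not predict the trial's data.

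The documents do not support reading this as a threat to the main safety conclusions. Weight, height and head circumference are other variables in a descriptive study with no testing, and the primary variables (TEAEs and serious TEAEs) are unaffected. Height and head circumference are a secondary matter: no post-Baseline table is planned, but the collection schedule is not in the SAP.

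**What to change.** In Section 8.4.1:

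1. Add body weight to the observed and change-from-Baseline table, using the Section 3.3 Baseline. Preferably show it also as an age- and sex-standardised z-score with its change, because raw kg rises with normal growth. State which growth chart applies at which age; Section 11 already cites growth charts.
2. Add a pre-BRV Baseline column, or a shift from Baseline, to the weight PCST table, so that newly flagged subjects are counted apart from those already outside the limits.
3. Secondary: summarise change in height and head circumference in the same way at the visits where the protocol collects them, and extend the weight Baseline rule in Section 3.3 to both.

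The cost is SAP wording, a few extra descriptive tables and some z-score programming. A weight growth reference is already needed for the flag, though z-scores require more than its 3% and 97% limits. No new data collection is involved.
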